8.2.2. Clinical Safety Laboratory Assessments

- Investigator sites should use local laboratories to determine patient eligibility and treatment decisions.
 - See Appendix 2 for the list of clinical laboratory tests to be performed and Section 1.3 (SoA) for the timing and frequency.
- All laboratory tests, with the exception of tumor markers, with values considered clinically significantly abnormal during participation in the study or until completion of V801 should be repeated until the values return to normal or baseline or are no longer considered clinically significant by the investigator or Lilly medical team.
 - If such values do not return to normal/baseline within a period of time judged reasonable by the investigator, the etiology should be identified and the sponsor notified.
 - All protocol-required laboratory assessments, as defined in Appendix 2, must be conducted in accordance with the laboratory manual and the SoA.

8.2.2.1. Hepatic Safety Monitoring

In study participants with baseline ALT/AST <1.5X ULN

If a study participant enrolled with baseline ALT/AST <1.5X ULN experiences elevated ALT/AST $\geq 3X$ ULN and elevated TBL $\geq 2X$ ULN, or ALT/AST $\geq 5X$ ULN liver testing (Appendix 4) including ALT, AST, TBL, direct bilirubin, gamma-glutamyl transferase, and creatine kinase should be repeated within 3 to 5 days to confirm the abnormality and to determine if it is increasing or decreasing. If the abnormality persists or worsens, clinical and laboratory monitoring and evaluation for possible causes of abnormal liver tests, should be initiated by the investigator in consultation with the study CRP/CRS. Monitoring of ALT, AST, and TBL should continue until levels normalize or return to approximate baseline levels.

In study participants with baseline ALT/AST $\geq 1.5X$ ULN

If a study participant enrolled with baseline ALT/AST $\geq 1.5X$ ULN experiences elevated ALT/AST $\geq 3X$ baseline or ALT/AST $\geq 2X$ baseline and TBL $\geq 2X$ ULN, liver testing (Appendix 4) including ALT, AST, TBL, direct bilirubin, gamma-glutamyl transferase, and creatine kinase should be repeated within 3 to 5 days to confirm the abnormality and to determine if it is increasing or decreasing. If the abnormality persists or worsens, clinical and laboratory monitoring and evaluation for possible causes of abnormal liver tests, should be initiated by the

investigator in consultation with the study CRP/CRS. Monitoring of ALT, AST, and TBL should continue until levels normalize or return to approximate baseline levels.

Hepatic data (Appendix 4) should be collected in the event that 1 (or more) of the following conditions is met for the patient during the course of the study:

- In patients enrolled with baseline ALT/AST <1.5X ULN:
 - a. Elevated ALT/AST ≥ 3 X ULN and elevated total bilirubin ≥ 2 X ULN
 - b. ALT/AST ≥ 5 X ULN on 2 consecutive tests.
- In patients enrolled with baseline ALT/AST ≥ 1.5 X ULN (regardless of whether or not they have hepatic metastasis):
 - a. Elevated ALT/AST ≥ 2 X baseline and elevated TBL ≥ 2 X ULN
 - b. Elevated ALT/AST ≥ 3 X baseline on 2 consecutive tests.
- All patients
 - a. Discontinuation from study treatment due to a hepatic event or abnormality of liver tests
 - b. Occurrence of a hepatic event considered to be a SAE.

8.2.2.2. Chylothorax and Chylous Ascites Monitoring

If a participant develops a pleural effusion or abdominal ascites or both while on selpercatinib, fluid sampling and testing should be considered as part of the management algorithm whenever possible. The etiology of this finding varies and distinguishing chylous fluid from malignant (as well as other causes such as infectious) may impact management significantly (for example, presumption of disease progression with premature discontinuation of therapy). Additionally, a diagnosis of chylous effusions or ascites or both may indicate a role for conservative measures such as fluid replacement, dietary alteration or medical therapy or both (for example, somatostatin analogue) prior to consideration of more invasive measures. Selpercatinib interruption and dose modification should follow the general strategy as outlined in Section 6.6 (Dose Modification), based upon severity of the event.

8.2.2.3. Renal Safety Monitoring

In vitro, selpercatinib is an inhibitor of the drug transporter MATE1 and may reduce the clearance of MATE1 substrates (for example, creatinine). Selpercatinib may increase serum creatinine due to inhibition of the renal tubular secretion transporter MATE1, without affecting glomerular function. Complementary markers such as blood urea nitrogen (BUN), cystatin C, or calculated glomerular filtration rate (GFR), which are not based on creatinine, may be considered to determine whether renal function is impaired.

8.2.2.4. Thyroid Function Monitoring

Hypothyroidism was reported in patients receiving selpercatinib in clinical trials. Monitor patients for hypothyroidism and treat as medically appropriate. Baseline laboratory measurement of thyroid function is recommended in all patients. Patients with preexisting hypothyroidism should be treated as per standard medical practice prior to the start of selpercatinib treatment. All

patients should be observed closely for signs and symptoms of thyroid dysfunction during selpercatinib treatment. Thyroid function should be monitored periodically throughout treatment with selpercatinib. Patients who develop thyroid dysfunction should be treated as per standard medical practice. However, patients could have an insufficient response to substitution with levothyroxine (T4), as selpercatinib may inhibit the conversion of levothyroxine to liothyronine (T3) and supplementation with liothyronine may be needed.

8.3. Adverse Events and Serious Adverse Events

The investigator should provide AE verbatim terms and then the terms will be mapped by Lilly or its designee to corresponding terminology within the Medical Dictionary for Regulatory Activities (MedDRA) Lower Level term (LLT) dictionary. The investigator will use Common Terminology Criteria for Adverse Events (CTCAE) version 5.0 to assign AE severity grades. Lilly recommends a slight modification when implementing the CTCAE V5.0. Post baseline grading for all laboratory values should be done per normal limit references, where specified, regardless of whether the assessment is normal or abnormal at baseline.

Investigators are responsible for monitoring the safety of participants who have entered this study and for alerting Lilly or its designee to any event that seems unusual, even if this event may be considered an unanticipated benefit to the participant.

The investigator is responsible for the appropriate medical care of participants during the study.

The investigator remains responsible for following, through an appropriate health care option, AEs that are serious or otherwise medically important, considered related to the investigational product or the study, or that caused the participant to discontinue the investigational product before completing the study. The participant should be followed until the event resolves, stabilizes with appropriate diagnostic evaluation, or is otherwise explained. The frequency of follow-up evaluations of the AE is left to the discretion of the investigator.

Lack of drug effect is not an AE in clinical studies, because the purpose of the clinical study is to establish treatment effect.

After the ICF is signed, study site personnel will record via CRF the occurrence and nature of each participant's pre-existing conditions, including clinically significant signs and symptoms of the disease under treatment in the study. In addition, site personnel will record any change in the condition(s) and any new conditions as AEs. Investigators should record their assessment of the potential relatedness of each AE to protocol procedure, investigational product, via CRF.

The investigator will interpret and document whether or not an AE has a reasonable possibility of being related to study treatment, study device, or a study procedure, taking into account the disease, concomitant treatment or pathologies.

A "reasonable possibility" means that there is a cause and effect relationship between the investigational product, study device and/or study procedure and the AE.

The investigator answers yes/no when making this assessment.

Care will be taken not to introduce bias when detecting AEs and/or SAEs. Open-ended and non-leading verbal questioning of the participant is the preferred method to inquire about AEs.

Planned surgeries and nonsurgical interventions should not be reported as AEs unless the underlying medical condition has worsened during the course of the study.

If a participant's investigational product is discontinued as a result of an AE, study site personnel must report this to Lilly or its designee via CRF, clarifying if possible, the circumstances leading to any dosage modifications, or discontinuations of treatment. Dose modifications and treatment discontinuation due to an AE should follow criteria defined in Section 6.6 (Dose Modifications). An independent review committee will review blinded data to determine which treatment discontinuations due to an AE meet the treatment failure event criteria for the primary analysis.

Only AEs reasonably possibly related to study procedures should be recorded in the eCRF, after signing the prescreening ICF. If an SAE occurs after signing the pre-screen ICF, the SAE should be reported to the sponsor as per SAE reporting requirements and timelines if it is considered reasonably possibly related to study procedures.

All AEs occurring after signing the main study ICF are recorded in the eCRF and assessed for serious criteria. The SAE reporting to the sponsor begins after the patient has signed the main study ICF and has received investigational product. However, if an SAE occurs after signing the main Study ICF, but prior to receiving investigational product, the SAE should be reported to the sponsor as per SAE reporting requirements and timelines if it is considered possibly related to study procedures.

Adverse events

- An AE is any untoward medical occurrence in a participant administered a pharmaceutical product and which does not necessarily have a causal relationship with the study intervention. An AE can therefore be any unfavourable and unintended sign (including an abnormal laboratory finding), symptom, or disease (new or exacerbated) temporally associated with the use of a medicinal (investigational) product, or investigational combination product, whether or not related to the medicinal (investigational) product or investigational combination product.
- An AE is any untoward medical occurrence, unintended disease or injury, or untoward clinical signs (including abnormal laboratory finding) in study participants, users, or other persons, whether or not related to the investigational device.

Events meeting the AE definition

- Any abnormal laboratory test results (hematology, clinical chemistry, or urinalysis) or other safety assessments, for example, ECG, radiological scans, and vital signs measurements, including those that worsen from baseline, considered clinically significant in the medical and scientific judgment of the investigator, that is, not related to progression of underlying disease.
- Exacerbation of a chronic or intermittent pre-existing condition including either an increase in frequency and/or intensity of the condition.
- New condition detected or diagnosed after study intervention administration even though it may have been present before the start of the study.
- Signs, symptoms, or the clinical sequelae of a suspected drug-drug interaction.

- Medication error, misuse, or abuse of IMP, including signs, symptoms, or clinical sequelae.
- Lack of efficacy or failure of expected pharmacological action per se will not be reported as an AE or SAE. Such instances will be captured in the efficacy assessments. However, the signs, symptoms, and/or clinical sequelae resulting from lack of efficacy will be reported as AE or SAE if they fulfill the definition of an AE or SAE.

Events **NOT** meeting the AE definition

- Any clinically significant abnormal laboratory findings or other abnormal safety assessments that are associated with the underlying disease, unless judged by the investigator to be more severe than expected for the participant's condition.
- The disease or disorder being studied or expected progression, signs, or symptoms of the disease or disorder being studied, unless more severe than expected for the participant's condition.
- Medical or surgical procedure, for example, endoscopy, appendectomy. The condition that leads to the procedure is the AE.
- Situations in which an untoward medical occurrence did not occur (social and/or convenience admission to a hospital).
- Anticipated day-to-day fluctuations of pre-existing disease(s) or condition(s) present or detected at the start of the study that do not worsen.

Serious Adverse Events

An SAE is any AE from this study that results in one of the following outcomes:

- death
- initial or prolonged inpatient hospitalization
- a life-threatening experience (that is, immediate risk of dying)
- persistent or significant disability/incapacity
- congenital anomaly/birth defect
- important medical events that may not be immediately life-threatening or result in death or hospitalization but may jeopardize the participant or may require intervention to prevent one of the other outcomes listed in the definition above. Examples of such medical events include allergic bronchospasm requiring intensive treatment in an emergency room or at home, blood dyscrasias or convulsions that do not result in inpatient hospitalization, or the development of drug dependency or drug abuse.

All AEs occurring after signing the ICF are recorded in the CRF and assessed for serious criteria. The SAE reporting to the sponsor begins after the participant has signed the ICF and has received investigational product. However, if an SAE occurs after signing the ICF, but prior to receiving investigational product, the SAE should be reported to the sponsor as per SAE reporting requirements and timelines (see Section 8.3.1) only if it is considered reasonably possibly related to study procedure.

Serious adverse events, including death, caused by disease progression should not be reported unless the investigator deems them to be possibly related to study treatment. Study site personnel must alert Lilly or its designee of any SAE within 24 hours of investigator awareness of the event via a sponsor-approved method. If alerts are issued via telephone, they are to be immediately followed with official notification on study-specific SAE forms. This 24-hour notification requirement refers to the initial SAE information and all follow-up SAE information. Participants with a serious hepatic adverse event should have additional data collected using the CRF.

Pregnancy (during maternal or paternal exposure to investigational product) does not meet the definition of an AE. However, to fulfill regulatory requirements any pregnancy should be reported following the SAE process to collect data on the outcome for both mother and fetus.

Investigators are not obligated to actively seek AEs or SAEs in subjects once they have discontinued and/or completed the study (the participant disposition CRF has been completed). However, if the investigator learns of any SAE, including a death, at any time after a subject has been discharged from the study, and he/she considers the event reasonably possibly related to the study treatment or study participation, the investigator must promptly notify Lilly.

Suspected Unexpected Serious Adverse Reactions

Suspected unexpected serious adverse reactions (SUSARs) are serious events that are not listed in the IB and that the investigator identifies as related to investigational product or procedure. United States 21 CFR 312.32 and European Union Clinical Trial Directive 2001/20/EC and the associated detailed guidances or national regulatory requirements in participating countries require the reporting of SUSARs. Lilly has procedures that will be followed for the identification, recording and expedited reporting of SUSARs that are consistent with global regulations and the associated detailed guidances.

8.3.1. Time Period and Frequency for Collecting AE and SAE Information

All SAEs will be recorded and reported to the sponsor or designee immediately and under no circumstance should this exceed 24 hours. The investigator will submit any updated SAE data to the sponsor within 24 hours of it being available.

8.3.2. Follow-up of AEs and SAEs

After the initial AE/SAE report, the investigator is required to proactively follow each participant at subsequent visits/contacts. All SAEs will be followed until resolution, stabilization, the event is otherwise explained, or the participant is lost to follow-up (as defined in Section 7.3).

8.3.3. Regulatory Reporting Requirements for SAEs

- Prompt notification by the investigator to the sponsor of a SAE is essential so that legal obligations and ethical responsibilities towards the safety of participants and the safety of a study intervention under clinical investigation are met.
- The sponsor has a legal responsibility to notify both the local regulatory authority and other regulatory agencies about the safety of a study intervention under clinical investigation. The sponsor will evaluate the reported SAEs, including confirmation of relatedness and assessment of expectedness. The sponsor has processes for safety reports

for identification, recording, and expedited reporting of SUSARs according to local regulatory requirements. The sponsor will comply with country-specific regulatory requirements relating to safety reporting to the regulatory authority, Institutional Review Boards (IRB)/Independent Ethics Committees (IEC), and investigators.

- An investigator who receives an investigator safety report describing a SAE or other specific safety information (e.g., summary or listing of SAEs) from the sponsor will review and then file it along with the Investigator's Brochure and will notify the IRB/IEC, if appropriate according to local requirements.

8.3.4. Pregnancy

- Details of all pregnancies in female participants and, if indicated, female partners of male participants will be collected after the start of study intervention and until the completion of V801.
- If a pregnancy is reported, the investigator should inform the sponsor within 24 hours of learning of the pregnancy and should follow the procedures outlined in Appendix 3.
- Abnormal pregnancy outcomes (e.g., spontaneous abortion, fetal death, stillbirth, congenital anomalies, ectopic pregnancy) are considered SAEs.
- Additional requirements for pregnancy testing during and after study intervention are located in Appendix 3.
- The investigator is responsible for review of medical history, menstrual history, and recent sexual activity to decrease the risk for inclusion of a woman with an early undetected pregnancy.

8.3.5. Cardiovascular and Death Events

Not applicable.

8.3.6. Complaint Handling

Lilly collects product complaints on investigational products and drug delivery systems used in clinical studies in order to ensure the safety of study participants, monitor quality, and to facilitate process and product improvements.

Participants will be instructed to contact the investigator as soon as possible if he or she has a complaint or problem with the investigational product so that the situation can be assessed.

8.4. Treatment of Overdose

Refer to the IB and/or product label for selpercatinib, cabozantinib, or vandetanib for available information on the signs, symptoms, and treatment of overdose.

8.5. Pharmacokinetics

At the visits and times specified in the SoA (Section 1.3), blood samples will be collected to determine the plasma concentrations of selpercatinib.

A maximum of 5 samples may be collected at additional time points during the study if warranted and agreed upon between both the investigator and sponsor. Instructions for the collection and handling of blood samples will be provided by the sponsor. The actual date and time [24-hour clock time] of each sampling and prior dose will be recorded.

Blood for PK assessment will be collected on C1D8, and at first day of each consecutive cycle up to Cycle 6 and should be collected regardless even if study drug will be held for the next cycle. Samples are to be drawn within 12 hours prior to dose, and exact time of sample collection should be recorded. In addition, time of previous dose should be recorded. Additional PK may also be assessed in patients when considered necessary by the Investigator to understand exposure in relationship to possible safety. Additional samples should be considered for patients experiencing selpercatinib-related drug hypersensitivity at onset of event, and at resolution of event.

Bioanalytical samples collected to measure investigational product concentration and metabolism and/or protein binding will be retained for a maximum of 2 years following last participant visit for the study. During this time, samples remaining after the bioanalyses may be used for exploratory analyses, such as metabolism, transport and/or protein binding work.

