| Physical function (EORTC IL19) | | | | | X | | | X | | Completed electronically by the patient each week, not site-administered except on C1D1 when this should be collected while patient is on site prior to first treatment dose. |
| HRQoL (EORTC QLQ-C30) | | | X | | | | X | X | X | Site-administered at D1 of each cycle using the device provided prior to study intervention, and during follow up at scheduled clinic visits until disease progression. If the patient completed their 30 day assessments (V201) and discontinued prior to crossing over, they will not need to complete the Visit 801 assessments. Starting with C16, obtain every 12 weeks in adult patients (Cycles 16, 19, 22, etc.). |

| Screening, On-Study, and Post-Study Treatment Follow-Up Schedule of Activities for Patients on Arm A and Arm B | | | | | | | | | | | |
|--|------------------------|----|------------------|-----|-----------|---------------------------------------|----------|-----------------------------------|----------------------------------|---|--|
| | Screening | | On-Treatment | | | Safety assessments prior to crossover | | Post-Study Treatment | | | Instructions |
| | | | Cycle = 28 days | | | (only for patients on Arm B) | | | | | |
| | (Day Relative to C1D1) | | Cycle 1 | | Cycle 2-n | V201 ^a | | Short-term follow-up ^a | Long term Follow-up ^b | | |
| | | | (±3 days) | | (±3 days) | Day 1-30 (±7 days) | 1-x days | (30 ± 7 days) | (90 ± 14 days) | | |
| ≤42 | ≤7 | D1 | D8 | D15 | D1 | N/A | N/A | V801 | V802-8XX | | |
| Procedure | | | | | | | | | | | |
| Health Status (EQ-5D-5L) | | | X | | | X | X | | X | X | Site-administered at D1 of each cycle prior to study intervention using the device provided and during follow up at scheduled clinic visits until disease progression. If the patient completed their 30-day assessments (V201) and discontinued prior to crossing over, they will not need to complete the Visit 801 assessments. Starting with C16, obtain every 12 weeks in adult patients (Cycles 16, 19, 22, etc.). |
| Blood sample for pharmacokinetics | | | | X | | See Instructions | | | | | Arm A only: Samples to be drawn pre-dose (-2 to 0 hour) in Cycles 1-6. See Section 8.5. |
| Whole Blood for genomic DNA (PGx) | | | X | | | | | | | | Sample can be collected at any time if not collected on C1D1. |

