| | Visit 300 (Day relative to start of treatment) | Visit 301 | | | Visit 302-n | | | |
| | | Cycle 1 | | | Cycle 2-n | | | |
| | | (±3 days) | | | (±3 days) | | | |
| ≤42 | D1 | D8 | D15 | D1 | V801 | V802-8XX | | |
| Procedure | | | | | | | | |
| Worst Pain NRS | | | X | | | X | | Completed electronically daily by the patient, not site-administered, except on C1D1 when this should be collected while patient is on site prior to first treatment dose. To be completed through 1 year of study treatment then discontinued. |
| Patient-reported AEs (PRO-CTCAE) | | X | X | X | X | X | | Completed electronically weekly by the patient, not site-administered, except on C1D1 when this should be collected while patient is on site prior to first treatment dose. |
| Patient-reported side-effect burden (FACT-GP5) | | X | X | X | X | X | | Completed electronically weekly by the patient, not site-administered, except on C1D1 when this should be collected while patient is on site prior to first treatment dose. |
| Physical function (EORTC IL19) | | X | X | X | X | X | | Completed electronically weekly by the patient, not site-administered, except on C1D1 when this should be collected while patient is on site prior to first treatment dose. |
| HRQoL (EORTC QLQ-C30) | | X | | | See Instructions | X | X | Site-administered at D1 of each cycle using the device provided, and during follow up at scheduled clinic visits until disease progression. Please collect at C1-n, D1 prior to study intervention. Starting with C16, obtain every 12 weeks in adult patients (Cycles 16, 19, 22, etc.). |
| Health Status (EQ-5D-5L) | | X | | | See Instructions | X | X | Site-administered at D1 of each cycle using the device provided and during follow up at scheduled clinic visits until disease progression. Please collect at C1-n, D1 prior to study intervention. Starting with C16, obtain every 12 weeks in adult patients (Cycles 16, 19, 22, etc.). |
| Blood sample for pharmacokinetics | | | X | | X | | | Samples to be drawn pre-dose (-2 to 0 hour) in Cycles 1-6. See Section 8.5. |

| Optional Crossover Treatment (for patients crossing over from Arm B to Arm A) | | | | | | | | |
|---|--|------------------|-----------|----|------------------|-----------------------------------|----------------------------------|--|
| | Crossover Screening | On-Treatment | | | | Post-Study Treatment | | Instructions |
| | | Cycle = 28 days | | | | Short-term follow-up ^a | Long term Follow-up ^b | |

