6.1. Study Intervention(s) Administered

A cycle is defined as 28 days in length with treatment on days 1 through 28 of each cycle, regardless of treatment arm assignment. A delay of the start of a cycle due to holiday, weekend, bad weather, or other unforeseen circumstances will be permitted for a maximum of 7 days or situations noted in Section 10.1.9 and not counted as a protocol deviation. Cycles should not be delayed for AEs. If needed for AEs, doses should be omitted within a cycle. Treatment should be initiated within 7 days of randomization.

Regardless of treatment arm, drug will initially be dispensed as a 28-day supply. For adult patients remaining on treatment after Cycle 15, drug will be dispensed as an 84-day supply, starting at Cycle 16.

Selpercatinib doses will be administered at approximately the same times on each day and BID dosing will be separated by approximately 12 hours (a minimum of 6 hours between consecutive doses). Selpercatinib can be taken with or without food. Cabozantinib or vandetanib will be administered at approximately the same time on each day. Cabozantinib should be taken without food; patients should not eat for at least 2 hours before and at least 1 hour after each dose. Vandetanib can be taken with or without food.

All patients will keep a daily diary to record dosing compliance, which will also be assessed at each clinic visit by means of a capsule count in the returned bottle(s). Late doses (i.e., 4 or more hours after scheduled time for selpercatinib) should be noted in the diary. Doses of selpercatinib that are late by more than 6 hours and doses of cabozantinib or vandetanib that are late by more than 12 hours should be skipped and recorded in the dosing diary as missed. Vomiting after dosing should be noted in the diary and a vomited dose should not be re dosed or replaced.

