8.7.6. Pharmacokinetic/Pharmacodynamic Analyses

Selpercatinib plasma concentrations will be summarized by descriptive statistics. Additional analysis utilizing the population pharmacokinetics (PK) approach may also be conducted if deemed appropriate and described in a separate SAP. The relationship between selpercatinib plasma exposure and selected efficacy and safety outcomes may be explored.

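### Protocol Section 8.5 and the schedules of activities give different windows for pre-dose PK samples (12 hours against 2 hours), and the SAP has no timing rule for its pre-dose summary

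*Protocol*

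**What the plan says.** **Sampling window.** Protocol Section 8.5 states: "Samples are to be drawn within 12 hours prior to dose". It also asks for the sampling time and the time of the previous dose, and it requires the sample even when drug will be withheld in the coming cycle. The main schedule (Section 1.3.2) states: "Arm A only: Samples to be drawn pre-dose (-2 to 0 hour) in Cycles 1-6. See Section 8.5". The crossover schedule (Section 1.3.4) has the same window: "Samples to be drawn pre-dose (-2 to 0 hour) in Cycles 1-6. See Section 8.5".

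**Cross-references.** The schedules refer the reader to Section 8.5, and Section 8.5 opens by referring back: "At the visits and times specified in the SoA (Section 1.3), blood samples will be collected to determine the plasma concentrations of selpercatinib". No sentence says which text governs.

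**Dosing.** Protocol Section 6.1 sets selpercatinib doses about 12 hours apart, with at least 6 hours between them.

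**Endpoint.** Protocol Section 3 and SAP Section 4.1 list a secondary endpoint of pre-dose plasma concentration on Cycle 1 Day 8 and on Day 1 of Cycles 2 to 6.

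**Analysis.** SAP Section 8.7.6 states: "Selpercatinib plasma concentrations will be summarized by descriptive statistics". It leaves population PK as something that may be done if judged appropriate, under a separate SAP. Protocol Section 9.4.5 plans both the descriptive summary and a population PK evaluation without that condition. SAP Section 8.7.6 gives no rule on sample timing.

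**The concern.** A window as long as the dosing interval does not restrict when a sample is taken. On the nominal schedule, a sample drawn 3 hours after a dose is 12 - 3 = 9 hours before the next one, so Section 8.5 accepts it as pre-dose although it may be near the peak. The schedules would reject it. Sites can follow either text and depart from the other.

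A descriptive table that pools such samples under one pre-dose label mixes different points of the concentration curve. Its average moves upward, and its spread then includes differences in sampling time between sites and visits as well as differences between patients. What is at stake is the interpretation of one descriptive secondary endpoint in patients receiving selpercatinib.

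**Working it through.** The plan gives no figure for this effect, so there is none to reproduce. The check compares the windows and then sizes the consequence.

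**Step 1: share of the dosing interval** (interval 12 h, Protocol Section 6.1)
- Schedules: 2/12 = 17%.
- Section 8.5: 12/12 = 100%.

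This ratio of 6 describes window width only. It is not an effect on the endpoint.

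**Step 2: half-life.** Protocol Section 6.5.4 equates 5 half-lives of selpercatinib with about 7 days. Half-life = 7 x 24 / 5 = 33.6 h, so k = ln 2 / 33.6 = 0.0206 per hour.

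**Step 3: upper bound.** With one compartment and instantaneous absorption, concentration early in the interval relative to its end is 2^(interval / half-life):
- 12 h before the next dose: 2^(12/33.6) = 1.28, or 28% above the end-of-interval level.
- 2 h before the next dose: 2^(2/33.6) = 1.04, or 4% above.

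**Step 4: with absorption.** For a steady-state one-compartment oral model with interval T = 12 h,

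C(t) is proportional to exp(-kt)/(1 - exp(-kT)) - exp(-ka t)/(1 - exp(-ka T)),

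and the quantity of interest is C(t)/C(T). The absorption rate ka is assumed to be 0.5 to 2 per hour. The half-lives of 24 h and 12 h are assumed and show sensitivity. Entries are percent above the end-of-interval level.

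| Half-life | 12 h window, maximum | 12 h window, mean if times are spread evenly | 2 h window, maximum |
|---|---|---|---|
| 33.6 h (implied by Section 6.5.4) | 14-23 | 9-12 | 4 |
| 24 h (assumed) | 21-33 | 13-18 | 6 |
| 12 h (assumed) | 46-78 | 28-40 | 12 |

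The steady-state assumption is reasonable at the first sample. Cycle 1 Day 8 is 7 days after the first dose, which is 5 implied half-lives, and 1 - 2^(-5) = 97%.

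**Step 5: which recorded time can classify a sample.** Both windows are measured back from the next dose, but Section 8.5 records the sampling time and the time of the previous dose. When the next dose is withheld, there may be no later dose to measure from. Only time since the previous dose is available for every sample. On the nominal schedule, the 2-hour window corresponds to 12 - 2 = 10 to 12 hours after the previous dose. At the shortest permitted spacing it corresponds to 6 - 2 = 4 to 6 hours.

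**The case against.** The strongest reply is that this is a wording inconsistency with little consequence. Section 8.5 itself sends the reader to the schedules for times, and both schedules agree on -2 to 0 hours. Actual sampling and prior-dose times are recorded, and Protocol Section 9.4.5 plans a population PK analysis, which can use samples at any time. The endpoint is descriptive, with no comparison between arms and no share of alpha.

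Much of this stands and limits the point. It does not remove it. The deferral to the schedules is followed in the same section by a different explicit window, and the schedules refer back. Population PK is optional in the SAP, so the only committed PK analysis is the descriptive summary, and no rule there uses the recorded times.

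A reader might go further and infer that the endpoint fails to measure trough levels. The documents do not support that wording: they call the endpoint pre-dose and never trough.

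A reader might also assume a peak-to-trough ratio of 1.5 to 3 and conclude that early samples overstate by 50-200%. That conflicts with the half-life implied by Section 6.5.4. In the instantaneous-absorption model of Step 3, a ratio of 1.5 needs a half-life of 12 / log2(1.5) = 20.5 h, and a ratio of 3 needs 12 / log2(3) = 7.6 h. Five of the latter are about 1.6 days, not 7.

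**Conclusion.** The inconsistency is real and is in the current text. It can raise the pre-dose summary and widen its spread, and the size is modest: about 14-23% for the worst-timed sample at the implied half-life, 9-12% on average if all samples were spread evenly over the interval, and about 4% at most if the schedules are followed.

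These figures rest on one-compartment kinetics at steady state, on assumed absorption rates, and on a half-life inferred from a rounded statement about holding drug around radiotherapy or surgery. Multi-compartment kinetics could give other values. The documents do not show how many samples would fall outside the 2-hour window, so the realised bias cannot be stated.

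The primary and key secondary endpoints are not touched. The correction is worth making because it is cheap and affects how a stated secondary endpoint is reported.

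**What to change.** 1. State one sampling window in Protocol Section 8.5 and in both schedules (Sections 1.3.2 and 1.3.4).
2. In SAP Section 8.7.6, define by recorded time since the previous dose which samples enter the pre-dose summary. This also classifies samples taken when the next dose is withheld. Report how many samples are excluded.
3. Use the remaining samples in population PK only, with their actual times.
4. Align SAP Section 8.7.6 with Protocol Section 9.4.5 on whether population PK is committed.

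The cost is wording in the two documents and a filter on times already recorded. Some samples would leave the descriptive table, and no new data need to be collected.
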